## **11. Subgroup analyses**

Due to the small sample size, no subgroup analyses are planned.

## **12. Interim analyses**

A single interim analysis was planned to be conducted at 50% recruitment. The results of the interim analysis were to be reviewed by the DMEC, using a Peto-Haybittle stopping rule ( $P < 0.001$ ) to recommend early termination of the trial due to harm. However, as the required number of patients was not fulfilled, the interim analysis could not be carried out.

## **13. Safety**

The number and percentage of Serious Adverse Events (SAEs) within 30 days (either from admission to PICU for early delivery of CPAP or from randomisation for children and infants randomised to standard care) will be reported. SAEs will be compared between treatment groups using Fisher's exact test.

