# 4.0 Trial Design

SCARF is a pragmatic, open, RCT in infants and children with severely impaired immunity and acute respiratory failure.

Eligible infants and children, for whom written informed consent is available, will be randomly allocated, in equal numbers, to receive either, admission to the PICU for early CPAP or standard care on the ward. All other care will be at the discretion of the treating clinician.

Trial participants will be followed up to 30 days post-randomisation for assessment of requirement for intubation and invasive mechanical ventilation (primary outcome) and for adverse events.

In addition, participants will be followed up at 90 days and one year post-randomisation for assessment of secondary outcomes (see below).

Participant flow through the trial is summarised in Figure 1.

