## 14.3 Recording and reporting procedures

All infants and children eligible for SCARF are critically ill and due to the complexity of their condition are at increased risk of experiencing AEs. Many of these events are expected as a result of the infant/child's medical condition and standard treatment received in the PICU, but may not be related to participation in the trial. Consequently, any AEs occurring as a result of the infant/child's medical condition or standard critical care treatment will not be reported. Pre-existing conditions do not qualify as AEs unless they worsen, but should be documented in the infant/child's medical notes.

All other AEs that occur between randomisation and 30 days post-randomisation must be recorded in the participant's medical notes and on the SCARF CRF. Information regarding date and time of event onset, severity and relatedness of the AE to trial treatment must be recorded (definitions below).

Those meeting the definition of a SAE (i.e. severity 3, 4 or 5 – see section 14.4) must, in addition, be recorded in the SAE Log and reported to the ICNARC CTU, using the trial specific SCARF SAE Reporting Form, by fax within **24 hours** of observing or learning of the SAE. All sections of the SAE Reporting Form must be completed.

The process for recording and reporting AEs and SAEs is summarised in Figure 2.

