# Appendix 1: Expected adverse events

Expected adverse events that could be observed in participants up to 30 days following randomisation:

- Pneumothorax
- Facial pressure sores
- Sinusitis
- New nosebleed
- Corneal irritation
- Headache
- Abdominal bloating/distension
- Aspiration

[This list is not exhaustive. If an adverse event, as defined in section 14.1, occurs this should be recorded and reported as described in section 14.0]

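### SAP 13 analyses serious adverse events only, so recorded events of severity 1 or 2, including those of the kinds listed in Protocol Appendix 1, have no planned summary by arm

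*SAP*

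**What the plan says.** SAP 13 plans two things: to report "The number and percentage of Serious Adverse Events (SAEs) within 30 days", and a test, "SAEs will be compared between treatment groups using Fisher's exact test". It mentions no other class of adverse event.

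The protocol's collection is wider. Section 4.0 gives adverse events as a purpose of the 30-day follow-up, and 11.6 lists them as a day-30 data item. Section 14.3 first exempts events arising from the child's medical condition or from standard treatment ("standard critical care treatment will not be reported"). It then states: "All other AEs that occur between randomisation and 30 days post-randomisation must be recorded in the participant's medical notes and on the SCARF CRF". Onset, severity and relatedness must be given for each, and events of severity 3, 4 or 5 go further, to the SAE log and the trials unit.

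Appendix 1 is introduced as "Expected adverse events that could be observed in participants up to 30 days following randomisation". It lists pneumothorax, facial pressure sores, sinusitis, new nosebleed, corneal irritation, headache, abdominal distension and aspiration, and sends any adverse event that occurs to section 14 for recording and reporting.

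**The concern.** The intervention is CPAP given before gas exchange requires it, for at least 12 hours a day over at least four consecutive days (Protocol 3.0 and 10.1). A family or clinician weighing early CPAP needs to know how well it was tolerated as well as whether it averted intubation. Protocol 2.0 itself warns that delivering CPAP to infants and young children can be difficult.

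Several Appendix 1 events look like effects of a mask or of positive pressure. Under 14.4, a complication that needs treatment but does not materially lengthen the stay is severity 2. A treated facial sore could well fall there. It would be recorded with its grade and relatedness and then appear in no planned result. A report that followed the SAP exactly could describe the arms as similar in harm without having looked at these events.

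**Working it through.** The documents give no figure for the safety analysis, so there is no stated number to reproduce. The check traces each grade of event from collection to analysis.

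**1. Route by severity (Protocol 14.3 and 14.4; SAP 13)**

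| Severity | Recorded to day 30 if not exempt | In the SAP 13 test | Any other planned result by arm |
|---|---|---|---|
| 1 mild | yes | no | none |
| 2 moderate | yes | no | none |
| 3 severe | yes | yes, pooled | none |
| 4 life-threatening | yes | yes, pooled | none |
| 5 fatal | yes | yes, pooled | mortality outcomes |

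**2. Other places where a comparison might sit.** Protocol 19.2 contains no adverse-event analysis. The SAP's dummy tables are 1 to 4 and 5a to 5j, which is 4 + 10 = 14 tables. None has a row for an adverse event or even an SAE, and none of the three proposed figures concerns safety. Protocol 14.8 to 14.10 send safety information to the oversight groups and non-expedited events to the ethics committee once a year. Neither route is a comparison by arm in the final analysis.

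**3. How much could be left out.** Let s be the share of affected children whose event is serious, counting one event per child. SAP 13 sees s and leaves out 1 − s: 90% if s = 10%, 80% if s = 20%, 50% if s = 50%. The documents do not give s.

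**4. Illustration on assumed rates.** Half the target is 148 ÷ 2 = 74 children. SAP 12 says the required number for the interim analysis at 50% recruitment was not reached. I take 37 per arm as a ceiling and show the planned 74 per arm beside it. Assume 5% of controls have a recorded Appendix 1 event, against 20% or 30% of the CPAP arm. Serious-event rates are s times these; for example, s = 10% gives 0.5% against 2% or 3%. The probability that Fisher's test gives P < 0.05 is

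Σᵢ Σⱼ Bin(i; n, p_control) × Bin(j; n, p_CPAP) × 1[Fisher P(i, j) < 0.05].

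| Events compared | 37 per arm: 20% / 30% | 74 per arm: 20% / 30% |
|---|---|---|
| all recorded | 36% / 78% | 75% / 98% |
| serious only, s = 10% | under 1% / under 1% | 0.3% / 1.7% |
| serious only, s = 20% | 0.2% / 1.5% | 4.0% / 16% |
| serious only, s = 50% | 7% / 28% | 33% / 72% |

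The serious-only rows contain Appendix 1 events alone. SAP 13 pools them with all other SAEs. With an assumed background of 10% in each arm, the case of 5% against 30% with s = 10% becomes 10.5% against 13%. The probability is then 2.5% at 37 per arm and 4.6% at 74. For a smaller excess, 5% against 10%, even the comparison of all recorded events reaches only 3.5% at 37 per arm. These figures show how visible an excess would be. They do not argue for adding significance tests.

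**5. Unit of the test.** SAP 13 speaks of the number and percentage of SAEs without saying whether events or children are counted. One child can have several SAEs, and Fisher's test needs one classification per child. The footnotes to the SAP's dummy tables define n and % as patients, so the child is the natural reading. The sentence needs clarifying; the method can stay.

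**The case against.** Protocol 19.2 promises no adverse-event analysis, so the SAP has dropped nothing. Non-serious events do reach the trials unit's monitoring and the annual ethics report. Both statements are correct, but neither gives a result by arm.

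A stronger objection concerns the quality of the data. The trial is open, one arm is observed in PICU and the other on the ward, and 14.3 exempts events of standard critical care. Control children may escalate to CPAP or BiPAP (Protocol 10.2 and 10.4). A site might treat a mask effect in such a child as exempt while recording the same effect in the CPAP arm. A comparison of all recorded events could then be biased against CPAP. This stands, and it limits the remedy to a descriptive table.

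A reader might infer that the listed events are never compared. That goes too far: any graded 3 to 5, which could include pneumothorax or aspiration, enter the SAE test, though not by type. Protocol 14.2 also makes an event serious if it prolongs hospitalisation, without the qualifier that 14.4 uses, so the boundary between severity 2 and serious is not sharp.

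A reader might also infer that the harm result will favour CPAP. The documents contain no event rates. Appendix 1 speaks of expected events in participants and does not attribute them to CPAP; that link is a reasonable inference and no more.

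**Conclusion.** The gap is real and moderate. Two of the five event grades, severity 1 and 2, are collected by requirement and have no planned summary by arm. Appendix 1 events graded 3 to 5 are analysed only within the pool of all SAEs. Non-serious harm from early CPAP may therefore be missed or understated.

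The conclusion rests on two readings: that SAP 13 is the complete safety plan, which the contents list and dummy tables support, and that 14.3's equation of serious with severity 3 to 5 governs the SAE count. The amount left out depends on s, which is unknown, and the probabilities above depend on assumed rates. The documents do not establish that the omission tilts the harm result towards CPAP, because differential recording could act the other way.

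**What to change.** Add to SAP 13, and to the SAP's dummy tables, one descriptive table by randomised arm with the child as the unit. It should give the number and percentage of children with:

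- at least one recorded adverse event;
- each Appendix 1 event;
- adverse events by severity grade;
- an event judged possibly related or more;
- at least one SAE.

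List total events separately. State that Fisher's test on SAEs compares children with at least one SAE.

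State one start for the 30-day window. SAP 13 counts "either from admission to PICU for early delivery of CPAP or from randomisation for children and infants randomised to standard care", whereas Protocol 14.3 starts recording at randomisation for everyone. That is a separate discrepancy, but the two passages must be reconciled before any safety table is produced.

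The cost is a paragraph and a table, from data that 14.3 already requires on the form. The downside is that open allocation, PICU against ward observation and the 14.3 exemption may make recording differ between arms. The text should say so and present the non-serious comparison as descriptive.

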#### **4. Sample size calculation**

Data submissions to the Paediatric Intensive Care Audit Network (PICANet), the national clinical audit for PICUs in the UK, reported a mean of 3.3 patients per month with severely impaired immunity admitted to GOSH PICU over an eight-year period (2003-10). Two thirds were admitted with respiratory failure as the primary reason for admission and 75% of these received mechanical ventilation. We estimated that a similar number experience acute respiratory distress on the ward fitting our inclusion criteria that do not require ICU admission. Therefore we expected to randomise around 4-5 participants per month and anticipated an intubation rate of around 35-40% in the control group. Assuming the same relative risk reduction (~60%) as observed in adult studies, a sample of 148 children (74 in each treatment group) was required to detect a reduction in intubation rate from 35% to 14% with 80% power and a type 1 error rate of 5% (two-sided).

At the Trial Steering Committee meeting in November 2014, the decision was taken, due to poor recruitment, to continue the study to the current planned end of patient recruitment (January 2016) but not to seek additional funding to extend recruitment beyond this date.

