#### **6. Analysis principles**

All analyses will be conducted by intention to treat. The patients will be analysed according to the treatment group they were randomised to, irrespective of whether the treatment allocated was received i.e. all patients will be included in the analysis, regardless of whether they have, or have not, adhered to the protocol. A two-sided p value of <0.05 will be taken to indicate a statistically significant result.

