## 9. Primary analysis

The number and percentage of patients requiring invasive mechanical ventilation 30 days following randomisation will be reported. Invasive mechanical ventilation by 30 days following randomisation will be compared between the treatment groups, unadjusted, using Fisher's exact test and reported as a relative risk with 95% confidence interval and as an absolute risk reduction with 95% confidence interval.

As a secondary analysis, the primary outcome will also be analysed using logistic regression adjusted for the following baseline covariates: age, weight, bone marrow transplantation and PIM2 score. Other covariates originally planned for inclusion in the adjusted analysis (cause of impaired immunity, suspected main cause of acute respiratory failure) will not be included in the model due to the smaller sample size. The results of the logistic regression model will be reported as an adjusted odds ratio with a 95% confidence interval. The unadjusted odds ratio will be presented for comparison.

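### SAEs get counts, percentages and a Fisher P value but no effect estimate or confidence interval, and with at most 73 children a non-significant result would say little about non-fatal harm

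*SAP*

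**What the plan says.** SAP section 13 begins with a descriptive summary: "The number and percentage of Serious Adverse Events (SAEs) within 30 days (either from admission to PICU for early delivery of CPAP or from randomisation". The second of these starting points is the control group's. One sentence of inference follows: "SAEs will be compared between treatment groups using Fisher's exact test". Section 13 contains nothing else. The general rule in SAP section 6 applies to it: "A two-sided p value of <0.05 will be taken to indicate a statistically significant result".

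Other outcomes are treated differently. In SAP section 9 the primary outcome is also tested by Fisher's exact test, but is "reported as a relative risk with 95% confidence interval and as an absolute risk reduction with 95% confidence interval". Sections 10.1 and 10.2 pair Fisher's test with a relative risk and 95% interval for mortality and for Level 2 or 3 support. Sections 10.3 to 10.5 give regression coefficients with 95% intervals. The Table 4 shell has an effect-estimate column with intervals for all of these, but no SAE row. None of the other table shells covers safety.

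On trial size, SAP section 4 states that "a sample of 148 children (74 in each treatment group) was required to detect a reduction in intubation rate from 35% to 14% with 80" per cent power. SAP section 12 adds: "A single interim analysis was planned to be conducted at 50% recruitment", and then that "as the required number of patients was not fulfilled, the interim analysis could not be carried out".

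**The concern.** The SAP uses the same test for SAEs as for its binary outcomes but leaves out the interval. That matters most where a null result is likely and easily over-read. In a small trial, a large P value for SAEs is compatible with no excess, a moderate excess or a large one. Only an interval shows which of these the data leave open.

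The harms at issue are mainly non-fatal. Protocol Appendix 1 lists, among expected events, pneumothorax, aspiration and facial pressure sores, and the mortality analyses do not capture these. The one formal look at harm, planned for half recruitment, was not made. SAEs were still to be monitored by the DMEC (Protocol section 18.4), but the final SAE comparison now carries more of the weight.

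**Working it through.** **1. The plan's own figure.** Inputs from SAP section 4: 35% v 14%, 80% power, two-sided 5%. The documents do not name the formula. The two-proportion formula gives

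n = [1.96·√(2·0.245·0.755) + 0.8416·√(0.35·0.65 + 0.14·0.86)]² / 0.21² = 64.7 per arm.

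The continuity correction gives (n/4)·[1 + √(1 + 4/(n·0.21))]² = 73.9, so 74 per arm and 148 in total. The stated figure reproduces. Exact power of Fisher's test at 74 per arm is 81.0%. This calculation is for intubation. The documents give no power or sample size for SAEs.

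**2. How many children.** Half of 148 is 74. That point was not reached, so at most 73 were recruited. This is an inference, since the SAP does not state the achieved number. Allocation was 1:1 (Protocol section 9), so the most favourable split is 36 and 37.

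**3. Chance of missing a doubling.** The documents give no SAE rate, so both the control rate p and the doubling are assumptions. For arms of n₁ (CPAP) and n₂ (control),

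miss = 1 − Σ Bin(a; n₁, 2p)·Bin(b; n₂, p),

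summed over all tables (a, b) with two-sided Fisher P < 0.05.

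| Control → CPAP | 36 v 37 | 37 v 36 | 20 v 20 | 74 v 74 (planned) |
|---|---|---|---|---|
| 2% → 4% | 99.3% | 99.8% | 99.9% | 97.9% |
| 5% → 10% | 93.1% | 96.3% | 98.3% | 87.4% |
| 10% → 20% | 80.2% | 85.0% | 92.8% | 68.3% |
| 20% → 40% | 56.3% | 59.6% | 80.8% | 29.5% |
| 30% → 60% | 30.5% | 31.2% | 65.3% | 4.8% |

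The 20 v 20 column only illustrates a smaller trial. Protocol section 14.3 leaves unreported any event attributed to the child's condition or to standard critical care, so low rates of reportable SAEs are plausible. Low rates are where the test is weakest.

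For scale, 80% power for a doubling needs about 219 per arm from a 10% control rate and 91 per arm from 20% (continuity-corrected formula).

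**4. What an interval would add.** Newcombe limits for the risk difference d = p₁ − p₂ use the Wilson limits (l, u) of each arm: lower = d − √[(p₁ − l₁)² + (u₂ − p₂)²], upper = d + √[(u₁ − p₁)² + (p₂ − l₂)²]. The examples are hypothetical.

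- 8/36 on CPAP v 4/37 on control: p₁ = 0.222 (Wilson 0.117 to 0.381), p₂ = 0.108 (0.043 to 0.247), d = 0.114.
  - Lower = 0.114 − √(0.105² + 0.139²) = −0.060.
  - Upper = 0.114 + √(0.159² + 0.065²) = 0.286.
  - Fisher P = 0.22, yet an excess of 28.6 percentage points is not excluded.
- 6/36 v 1/37: P = 0.056; difference +14.0 points (−0.2 to 29.3).
- 0/36 v 0/37: P = 1.00; the upper limit is 1.96²/(36 + 1.96²) = 3.84/39.84, an excess of 9.6 points.

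In each case the P value alone conveys neither the estimate nor the limit.

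**The case against.** The strongest reply has five parts.

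- **Harm is not assessed by SAEs alone.** A reader might infer that the Fisher test is the trial's only safety analysis. It is not. Death is an SAE criterion (Protocol section 14.2), and SAP section 10.1 gives mortality at four time points a relative risk with a 95% interval, adjusted regression and survival curves. PELOD differences also carry intervals. This stands, and limits the point to the SAE comparison and mainly to non-fatal harm.
- **No claim of safety is planned.** A reader might infer that P above 0.05 would be presented as proof that early CPAP is safe. No section says so: SAP section 6 defines only what a significant result is, and there is no safety hypothesis or margin. The plan leaves that misreading open; it does not commit to it.
- **The omission has no built-in direction.** A reader might infer that it favours CPAP. The two-sided test is just as weak against a benefit: a true halving from 20% to 10% is missed 80–85% of the time at the same arm sizes.
- **An interval adds no power.** This is correct. Low power comes from poor recruitment, not from choosing Fisher's test. The miss rates show why a P value alone is uninformative here, and the interval makes that imprecision visible.
- **Readers could compute the interval from the reported counts.** Only if the counts are of children. SAP section 13 speaks of the number and percentage of SAEs and does not say whether children or events are counted, although Fisher's test needs children. SAP section 1 also gives the avoidance of data-derived decisions as the reason for fixing analyses in advance, so the estimate belongs in the plan.

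**Conclusion.** The point holds in this limited form: SAEs are the one planned between-group comparison of outcome or safety without an effect estimate and interval, in a trial too small for the P value to carry the conclusion. That SAP section 13 and Table 4 omit them is plain on their face and needs no assumption.

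The size does rest on assumptions: at most 73 children, split as evenly as possible; a true doubling; and control SAE rates chosen for illustration. From 5%, 10%, 20% and 30%, the test misses a doubling about 93–96%, 80–85%, 56–60% and 31% of the time. The figure exceeds 99% from 2%, is about 17% from 35%, and at a given rate rises with fewer children. No single range should be quoted without its assumed rate. This is a cheap and worthwhile correction to what the trial can say about harm. It does not undermine the primary analysis.

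**What to change.** Revise SAP section 13 along these lines:

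- Report, by randomised group, the number and percentage of children with at least one SAE.
- Give the risk difference with a 95% interval by a score method such as Newcombe's, and the relative risk with a 95% interval. If the control arm has no events the relative risk is undefined, and the risk difference stands alone.
- Keep Fisher's P value as supplementary.
- State that a non-significant result is not evidence of no excess harm, and report the largest excess with early CPAP that the upper 95% limit leaves open.
- Add the matching SAE row to Table 4.

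One neighbouring matter needs separate attention. SAP section 13 starts the 30-day window at PICU admission in one arm and at randomisation in the other, whereas Protocol section 14.3 counts from randomisation. The two should be reconciled so that the interval compares like periods.

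The cost is a few sentences and one table row, with no new data or patients. The downside is small: the interval will be wide, so the safety statement will look less certain.

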## Appendix 1: Dummy tables and figures

### Proposed tables

i. Table 1: Comparison of baseline characteristics by treatment group

	Variables	Early CPAP	Usual treatment
		N=XX	N=XX
Age group	0-11 months, n (%)	XX (XX.X)	XX (XX.X)
	12 months or older, n (%)	XX (XX.X)	XX (XX.X)
	[N]	[XX]	[XX]
Age (months)	mean (SD)	XX.X (XX.X)	XX.X (XX.X)
	median (IQR)	XX (XX, XX)	XX (XX, XX)
	[N]	[XX]	[XX]
Gender	Male, n (%)	XX (XX.X)	XX (XX.X)
	Female, n (%)	XX (XX.X)	XX (XX.X)
	[N]	[XX]	[XX]
Weight (kg)	mean (SD)	XX.X (XX.X)	XX.X (XX.X)
	median (IQR)	XX.X (XX.X, XX.X)	XX.X (XX.X, XX.X)
	[N]	[XX]	[XX]
Acute respiratory failure criteria met	Acute respiratory failure, n (%)	XX (XX.X)	XX (XX.X)
	Acute on chronic respiratory failure, n (%)	XX (XX.X)	XX (XX.X)
	[N]	[XX]	[XX]
Bone marrow transplant	Yes, n (%)	XX (XX.X)	XX (XX.X)
	No, n (%)	XX (XX.X)	XX (XX.X)
	[N]	[XX]	[XX]
Cause of impaired immunity*	High risk of severe neutropenia, n (%)	XX (XX.X)	XX (XX.X)
	Severe immunodeficiency, n (%)	XX (XX.X)	XX (XX.X)
	Haemophagocytic lymphohistiocytosis, n (%)	XX (XX.X)	XX (XX.X)
	Undergoing bone marrow transplantation, n (%)	XX (XX.X)	XX (XX.X)
	Other condition/therapy, n (%)	XX (XX.X)	XX (XX.X)
[N]	[XX]	[XX]	
Suspected main cause of acute respiratory failure	Viral pneumonitis, n (%)	XX (XX.X)	XX (XX.X)
	Bacterial chest infection, n (%)	XX (XX.X)	XX (XX.X)
	Graft-versus-host disease, n (%)	XX (XX.X)	XX (XX.X)
	Fluid overload, n (%)	XX (XX.X)	XX (XX.X)
	Veno-occlusive disease, n (%)	XX (XX.X)	XX (XX.X)
	Other condition/therapy*, n (%)	XX (XX.X)	XX (XX.X)
[N]	[XX]	[XX]	
PIM2r score	mean (SD)	XX.X (XX.X)	XX.X (XX.X)
	median (IQR)	XX (XX, XX)	XX (XX, XX)
	[N]	[XX]	[XX]
Supplemental O2 requirement (pre-acute respiratory failure)	No, n (%)	XX (XX.X)	XX (XX.X)
	Yes, n (%)	XX (XX.X)	XX (XX.X)
	[N]	[XX]	[XX]

\* patients may have more than one cause of impaired immunity; n: number of patients; %: percentage of patients; N: total number of patients; SD: standard deviation; IQR: interquartile range

ii. Table 2: Comparison of clinical management by treatment group

Variables		Early CPAP	Usual treatment
		N=XX	N=XX
PICU admission	No, n (%)	XX (XX.X)	XX (XX.X)
	Yes, n (%)	XX (XX.X)	XX (XX.X)
	[N]	[XX]	[XX]
Length of stay in PICU (days)	mean (SD)	XX.X (XX.X)	XX.X (XX.X)
	median (IQR)	XX.X (XX.X, XX.X)	XX.X (XX.X, XX.X)
	[N]	[XX]	[XX]
CPAP (Level 2 respiratory support) received	No, n (%)	XX (XX.X)	XX (XX.X)
	Yes, n (%)	XX (XX.X)	XX (XX.X)
	[N]	[XX]	[XX]
Length of stay in acute hospital (days)	mean (SD)	XX.X (XX.X)	XX.X (XX.X)
	median (IQR)	XX (XX, XX)	XX (XX, XX)
	[N]	[XX]	[XX]

n: number of patients; %: percentage of patients; N: total number of patients; SD: standard deviation; IQR: interquartile range

iii. Table 3: Protocol adherence by treatment group

	Early CPAP	Usual treatment
	N=XX	N=XX
Protocol deviations		
Did not start CPAP within 24 hours	XX (XX.X)	N/A
CPAP not received for specified time period*	XX (XX.X)	N/A
Higher level of respiratory support received without clear clinical criteria documented for escalation	XX (XX.X)	XX (XX.X)
High Flow Humidified Oxygen (HFHO) received	XX (XX.X)	XX (XX.X)
Overall adherence, n (%)	XX (XX.X)	XX (XX.X)

\*other than due to escalation of respiratory support; n: number of patients; %: percentage of patients; N: total number of patients; SD: standard deviation; IQR: interquartile range

iv. Table 4: Comparison of outcomes by treatment group

Outcomes	Early CPAP	Usual treatment	Effect estimate (95% CI)	P value
	N=XX	N=XX		
Primary outcome				
Requirement for intubation and invasive mechanical ventilation (Level 4 respiratory support) within 30 days*, n (%)	XX (XX.X)	XX (XX.X)	Relative risk: X.XX (X.XX, X.XX)	0.XXX
			Absolute risk reduction: X.X (X.X, X.X)	
			Odds ratio: X.XX (X.XX, X.XX)	
			Adjusted odds ratio: X.XX (X.XX, X.XX)	0.XXX
Secondary outcomes				
Maximum PELOD score  at 30 days*, mean (SD)	XX.X (XX.X)	XX.X (XX.X)	Mean difference: X.X (X.X, X.X)	0.XXX
			Adjusted mean difference: X.X (X.X, X.X)	0.XXX
Aggregate PELOD score  at 30 days*, mean (SD)	XX.X (XX.X)	XX.X (XX.X)	Mean difference: X.X (X.X, X.X)	0.XXX
			Adjusted mean difference: X.X (X.X, X.X)	0.XXX
Mortality at 30 days*, n (%)	XX (XX.X)	XX (XX.X)	Odds ratio: X.XX (X.XX, X.XX)	0.XXX
			Adjusted odds ratio: X.XX (X.XX, X.XX)	0.XXX
Requirement for Level 2 or Level 3 respiratory support within 30 days*, n (%)	XX (XX.X)	XX (XX.X)	Odds ratio: X.XX (X.XX, X.XX)	0.XXX
			Adjusted odds ratio: X.XX (X.XX, X.XX)	0.XXX
Days free from any ventilator support at 30 days*, mean (SD)	XX.X (XX.X)	XX.X (XX.X)	Mean difference: X.X (X.X, X.X)	0.XXX
			Adjusted mean difference: X.X (X.X, X.X)	0.XXX
Days free from supplemental oxygen at 30 days*, mean (SD)	XX.X (XX.X)	XX.X (XX.X)	Mean difference: X.X (X.X, X.X)	0.XXX
			Adjusted mean difference: X.X (X.X, X.X)	0.XXX
Hospital mortality, n (%)	XX (XX.X)	XX (XX.X)	Odds ratio: X.XX (X.XX, X.XX)	0.XXX
			Adjusted odds ratio: X.XX (X.XX, X.XX)	0.XXX
Mortality at 90 days*, n (%)	XX (XX.X)	XX (XX.X)	Odds ratio: X.XX (X.XX, X.XX)	0.XXX
			Adjusted odds ratio: X.XX (X.XX, X.XX)	0.XXX
Mortality at one year*, n (%)	XX (XX.X)	XX (XX.X)	Odds ratio: X.XX (X.XX, X.XX)	0.XXX
			Adjusted odds ratio: X.XX (X.XX, X.XX)	0.XXX

\*post-randomisation; n: number of patients; %: percentage of patients; SD: standard deviation

- v. Table 5a: Logistic regression model for requirement of invasive mechanical ventilation at 30 days post-randomisation

Variables	Odds ratio	95% CI	P-value
Treatment			
Usual treatment	1		
Early CPAP	X.XX	X.XX, X.XX	0.XXX
Age (per year)	X.XX	X.XX, X.XX	0.XXX
Weight (per 5kg)	X.XX	X.XX, X.XX	0.XXX
Bone marrow transplantation			
No	1		
Yes	X.XX	X.XX, X.XX	0.XXX
PIM2r score (per point)	X.XX	X.XX, X.XX	0.XXX

- vi. Table 5b: Linear regression model for maximum PELOD score at 30 days post-randomisation

Variables	Coefficient	95% CI	P-value
Constant	X.XX	X.XX, X.XX	0.XXX
Treatment			
Usual treatment	0		
Early CPAP	X.XX	X.XX, X.XX	0.XXX
Age (per year)	X.XX	X.XX, X.XX	0.XXX
Weight (per 5kg)	X.XX	X.XX, X.XX	0.XXX
Bone marrow transplantation			
No	0		
Yes	X.XX	X.XX, X.XX	0.XXX
PIM2r score (per point)	X.XX	X.XX, X.XX	0.XXX

- vii. Table 5c: Linear regression model for aggregate PELOD score at 30 days post-randomisation

Variables	Coefficient	95% CI	P-value
Constant	X.XX	X.XX, X.XX	0.XXX
Treatment			
Usual treatment	0		
Early CPAP	X.XX	X.XX, X.XX	0.XXX
Age (per year)	X.XX	X.XX, X.XX	0.XXX
Weight (per 5kg)	X.XX	X.XX, X.XX	0.XXX
Bone marrow transplantation			
No	0		
Yes	X.XX	X.XX, X.XX	0.XXX
PIM2r score (per point)	X.XX	X.XX, X.XX	0.XXX

viii. Table 5d: Logistic regression model for mortality at 30 days post-randomisation

Variables	Odds ratio	95% CI	P-value
Treatment			
Usual treatment	1		
Early CPAP	X.XX	X.XX, X.XX	0.XXX
Age (per year)	X.XX	X.XX, X.XX	0.XXX
Weight (per 5kg)	X.XX	X.XX, X.XX	0.XXX
Bone marrow transplantation			
No	1		
Yes	X.XX	X.XX, X.XX	0.XXX
PIM2r score (per point)	X.XX	X.XX, X.XX	0.XXX

ix. Table 5e: Logistic regression model for requirement for Level 2 or Level 3 respiratory support within 30 days post-randomisation

Variables	Odds ratio	95% CI	P-value
Treatment			
Usual treatment	1		
Early CPAP	X.XX	X.XX, X.XX	0.XXX
Age (per year)	X.XX	X.XX, X.XX	0.XXX
Weight (per 5kg)	X.XX	X.XX, X.XX	0.XXX
Bone marrow transplantation			
No	1		
Yes	X.XX	X.XX, X.XX	0.XXX
PIM2r score (per point)	X.XX	X.XX, X.XX	0.XXX

x. Table 5f: Linear regression model for days free from any ventilator support at 30 days post-randomisation

Variables	Coefficient	95% CI	P-value
Constant	X.XX	X.XX, X.XX	0.XXX
Treatment			
Usual treatment	0		
Early CPAP	X.XX	X.XX, X.XX	0.XXX
Age (per year)	X.XX	X.XX, X.XX	0.XXX
Weight (per 5kg)	X.XX	X.XX, X.XX	0.XXX
Bone marrow transplantation			
No	0		
Yes	X.XX	X.XX, X.XX	0.XXX
PIM2r score (per point)	X.XX	X.XX, X.XX	0.XXX

- xi. Table 5g: Linear regression model for days free from supplemental oxygen at 30 days post-randomisation

Variables	Coefficient	95% CI	P-value
Constant	X.XX	X.XX, X.XX	0.XXX
Treatment			
Usual treatment	0		
Early CPAP	X.XX	X.XX, X.XX	0.XXX
Age (per year)	X.XX	X.XX, X.XX	0.XXX
Weight (per 5kg)	X.XX	X.XX, X.XX	0.XXX
Bone marrow transplantation			
No	0		
Yes	X.XX	X.XX, X.XX	0.XXX
PIM2r score (per point)	X.XX	X.XX, X.XX	0.XXX

- xii. Table 5h: Logistic regression model for hospital mortality

Variables	Odds ratio	95% CI	P-value
Treatment			
Usual treatment	1		
Early CPAP	X.XX	X.XX, X.XX	0.XXX
Age (per year)	X.XX	X.XX, X.XX	0.XXX
Weight (per 5kg)	X.XX	X.XX, X.XX	0.XXX
Bone marrow transplantation			
No	1		
Yes	X.XX	X.XX, X.XX	0.XXX
PIM2r score (per point)	X.XX	X.XX, X.XX	0.XXX

- xiii. Table 5i: Logistic regression model for mortality at 90 days post-randomisation

Variables	Odds ratio	95% CI	P-value
Treatment			
Usual treatment	1		
Early CPAP	X.XX	X.XX, X.XX	0.XXX
Age (per year)	X.XX	X.XX, X.XX	0.XXX
Weight (per 5kg)	X.XX	X.XX, X.XX	0.XXX
Bone marrow transplantation			
No	1		
Yes	X.XX	X.XX, X.XX	0.XXX
PIM2r score (per point)	X.XX	X.XX, X.XX	0.XXX

[figure not shown]
xiv. Table 5j: Logistic regression model for mortality at one year post-randomisation

Variables	Odds ratio	95% CI	P-value
Treatment			
Usual treatment	1		
Early CPAP	X.XX	X.XX, X.XX	0.XXX
Age (per year)	X.XX	X.XX, X.XX	0.XXX
Weight (per 5kg)	X.XX	X.XX, X.XX	0.XXX
Bone marrow transplantation			
No	1		
Yes	X.XX	X.XX, X.XX	0.XXX
PIM2r score (per point)	X.XX	X.XX, X.XX	0.XXX

